7. SAFETY ANALYSIS

Safety analyses to be performed include: adverse events, physical examination, and vital signs.

7.1 Extent of Exposure

This is not applicable since no investigational drug will be used in the study.

7.2 Adverse Events

Adverse events will be recorded throughout the study, but only those occurring within the first 90 days post-transplant will be reported to the Sponsor, unless they are considered SAEs. All SAEs will be recorded and reported to the Sponsor throughout the Analysis Phase. Adverse events and medical conditions will be coded using the Medical Dictionary for Regulatory Activities (MedDRA) coding dictionary.

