2.2 Secondary Objective(s)

The secondary objectives of this study are to evaluate the short-term safety of subjects receiving a lung transplant where the lung(s) has been perfused via the TES performed by the Sponsor by assessment of the following:

- PGD Score (Grades 0-3) measured at 0, 24, 48 and 72 hours post-transplant
- Time to first extubation
- Intensive care unit (ICU) length of stay (LOS), measured as total number of days post-transplant in the ICU until first hospital discharge, inclusive of ICU readmissions during that hospitalization
- Hospital LOS measured as total number of days in the hospital prior to discharge post-transplant
- Total preservation time (TPT), defined as the elapsed time between first allograft lung removal from cold storage time prior to transplant in the recipient and the donor aortic cross clamp time at procurement
- Assessment of the overall safety of TES lung transplants during subject's participation in the study, as reported through adverse events (AEs).

The above information will also be collected on patients enrolled in a contemporaneous control group to provide context for EVLP results and to inform control measures for future research.

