6.13.2 Performing Adverse Events Assessments or Recording of Adverse Events

The Study Center staff will record and monitor all AEs throughout the Analysis Phase of the study (1-year post-intervention), from the time of transplanted lung reperfusion until the end of the subject's study participation. At all study visits, reports of AEs will be elicited by a verbal probe ("How are you feeling?"). Subjects will be encouraged to contact the Study Center to report an AE at any time. Appropriate measures, including medical intervention and/or procedures, will be instituted if clinically indicated at the discretion of the Investigator.

All AEs occurring during the study must be documented, and any AEs occurring during the first 90 days post-transplant must be reported in the CRFs for AEs. For each AE, the Investigator will evaluate the severity and seriousness, as well as the relationship of the AE to the device and procedure. Information relating to the AE, such as onset and cessation date and times, seriousness, severity, relationship to device/procedure, action taken, and outcome will also be documented in the subject's source documentation for assessment. Where possible, AEs should be recorded using standard medical terminology. If several signs or symptoms are clearly related to a medically defined diagnosis or syndrome, the diagnosis or syndrome should be recorded, not the individual signs and symptoms.

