6.13.3 Timing of Adverse Event Collection

All AEs are collected from the time of transplanted lung reperfusion through subject participation duration (1 year post-operative). Reporting procedures are described in Section 6.13.7.

Subjects with AEs that are ongoing at the subject's last Study Center visit must be followed until resolution or for 30 days after the subject's last Study Center visit, whichever comes first. Adverse events that are recorded during the 7 days following the subject's last Study Center visit will be followed until resolution or for up to the 30 days after the subject's last Study Center visit, whichever comes first. All AEs that are ongoing after follow-up for 30 days' time will be recorded as ongoing. The Investigator is expected to provide or arrange appropriate supportive care for any subject with ongoing AE(s).

Serious adverse events (SAEs) should be followed until they resolve or the event or their sequelae stabilize. Supplemental measurements and/or evaluations may be necessary to investigate fully the nature and/or causality of an AE or SAE. Such supplementary assessments may include additional laboratory tests, diagnostic procedures, or consultation with other healthcare professionals. The subject's source documents and CRFs for AEs should be updated with any new or additional information as appropriate.

If the subject reports or the Investigator learns of any new SAE that occurs up to 30 days after the subject's last clinical site visit, the clinical site personnel will ensure that these data are reported on the AE CRF.

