4. GENERAL CONSIDERATIONS FOR DATA ANALYSIS

No statistical hypotheses will be tested in this study. Rather, displays of study results – regarding intervention-related safety among the transplant groups (EVLP or Control) – will primarily utilize descriptive statistics, as noted below.

Unless otherwise specified, continuous variables will be summarized by presenting the number of non-missing observations, mean, standard deviation, median, minimum, and maximum. Categorical variables will be summarized by presenting the number of subjects and percentage for each category.

Summary results will be provided for each transplant group. All tabulations will be based on pooled data across centers. Analyses will be performed primarily on data collected during the Analysis Phase (1-year post-intervention). The database will be locked for analysis of endpoints after the last subject completes his/her study visit at Year 1, and all queries have been resolved. The Long-term Follow-up data will be summarized when the study has completed in support of

long-term evaluation.

Analyses will be performed using SAS for Windows statistical software, version 9.2 or higher (SAS, Cary, NC), except where other software may be deemed more appropriate.

CTI Clinical Trial and Consulting Services (Cincinnati, OH) will perform all statistical analyses.

Subject data will be listed, sorted by transplant group and subject number.

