7.2.1 Intervention-emergent Adverse Events

Intervention-emergent AEs will be defined as those events, which are newly occurring or worsening from Baseline (Day 0). In all cases, only intervention-emergent AEs will be summarized.

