7.2.5 Adverse Event Summaries

Adverse events and medical conditions will be coded using the Medical Dictionary for Regulatory Activities (MedDRA) coding dictionary. For intervention-emergent AEs, the following will be summarized and presented by Transplant Group for the FAS:

- i. An overall summary of Intervention-emergent AEs, which includes:
 - a. the number and percentage of subjects experiencing an intervention-emergent AE
 - b. the number and percentage of subjects experiencing an intervention-emergent AE by greatest severity
 - c. the number and percentage of subjects experiencing an intervention-emergent AE by strongest relationship to lung transplant
 - d. the number and percentage of subjects experiencing an intervention-emergent AE by strongest relationship to study intervention
 - e. the number and percentage of subjects experiencing an Intervention-emergent SAE
- ii. the number and percentage of subjects experiencing an intervention-emergent AE by SOC and PT
- iii. the number and percentage of subjects experiencing an intervention-emergent AE by SOC, PT, and strongest relationship to study intervention
- iv. the number and percentage of subjects experiencing an intervention-emergent AE by SOC, PT, and greatest severity
- v. the number and percentage of subjects experiencing an intervention-emergent SAE by SOC and PT
- vi. the number and percentage of subjects experiencing an intervention-emergent AE leading to study withdrawal by SOC and PT

In the overall summary of intervention-emergent AEs table (i), besides tabulating the number and percentage of subjects, the total number of Intervention-emergent AE episodes will also be provided. If a subject has repeated episodes of a particular Intervention-emergent AE, all episodes will be counted in the summary table.

In the remaining summary tables, the incidence of intervention-emergent AEs will be calculated by dividing the number of subjects who have experienced the event by the total number of subjects in the FAS. Thus, the incidence of intervention-emergent AEs is shown in terms of the total number of subjects and not in terms of the total number of episodes. If a subject has repeated episodes of a particular intervention-emergent AE, only the most severe episode, or the episode with the strongest causal relationship to study intervention, will be counted in the summary tables.

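### The all-AE tables in SAP 7.2.5 mix a 90-day window for non-serious events with a 1-year window for SAEs, so their percentages are neither 90-day nor 1-year incidences

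*SAP*

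**What the plan says.** **Reporting windows.** SAP 7.2 states that "only those occurring within the first 90 days post-transplant will be reported to the Sponsor, unless they are considered SAEs". It continues: "All SAEs will be recorded and reported to the Sponsor throughout the Analysis Phase". Protocol 9.9.1 sets the same split. Protocol 6.13.2 requires all AEs to be documented, but adds that "any AEs occurring during the first 90 days post-transplant must be reported in the CRFs for AEs". Protocol 6.13.7 repeats the split for the annual report to FDA.

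**Length of the Analysis Phase.** SAP 4: "Analyses will be performed primarily on data collected during the Analysis Phase (1-year post-intervention").

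**Events summarised.** SAP 7.2.1: "Intervention-emergent AEs will be defined as those events, which are newly occurring or worsening from Baseline (Day 0"). This gives a start and no end.

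**Tables.** SAP 7.2.5 lists:
- an overall summary: any AE (i.a), greatest severity (i.b), relationship to transplant (i.c), relationship to study intervention (i.d) and any SAE (i.e);
- AEs by SOC and PT (ii), and by SOC, PT and relationship (iii);
- (iv) "the number and percentage of subjects experiencing an intervention-emergent AE by SOC, PT, and greatest severity";
- SAEs by SOC and PT (v), and AEs leading to withdrawal (vi).

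The denominator is every subject in the full analysis set. Neither SAP 7.2.5 nor SAP 4.3 (Assessment Windows) restricts AEs by onset day.

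**Use of the results.** Protocol 2.2 lists as a secondary item "Assessment of the overall safety of TES lung transplants during subject's participation in the study, as reported through adverse events (AEs"). SAP 9 says the Control group is there partly to estimate parameters for the design of later studies.

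**The concern.** A percentage of subjects with an event means something only over a stated period. Here the period depends on whether the event was serious. A non-serious event with onset on Day 120 is not in the tables; a serious event of the same preferred term on the same day is. A row in table ii is therefore a 90-day figure for its non-serious part and a 1-year figure for its serious part, and nothing in the SAP tells the reader so.

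The rule for repeated episodes carries the mixture into single subjects. A mild event on Day 10 is replaced in table iv by a severe SAE of the same term on Day 200, but not by a severe non-serious one.

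AE-based safety is a named secondary endpoint, and the Control figures are meant to be reused. A later team could take a row from table ii as a 90-day or a 1-year rate, and either would be wrong.

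**Working it through.** **1. What each window contains.** The documents give no AE rates, so there is no stated figure to reproduce. What follows first needs no assumption about rates. Days 91 to 365 are 365 − 90 = 275 days, and 275/365 = 75% of the Analysis Phase.

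| Onset | Non-serious AE | SAE |
|---|---|---|
| Day 0 to 90 | counted | counted |
| Day 91 to 1 year | not reported, so not counted | counted |

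**2. Direction.** The events counted contain all reported 90-day events and are a subset of those that full 1-year reporting would give. For any row that asks whether a subject had the event at all (i.a, ii, and the any-event total for each term in iii and iv):

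90-day incidence ≤ tabulated percentage ≤ 1-year incidence.

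The first inequality is strict when some subject's first counted event is a late SAE. The second is strict when some subject's only event is late and non-serious. The same bounds hold for the top severity category. The lower categories of a greatest-severity table can move either way, because a late event can move a subject from mild to severe.

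**3. Size for one event type (assumed rates).** Let the true 1-year incidence be 30%, so the cumulative hazard is H = −ln(0.70) = 0.3567. Let a be the part to Day 90, b = H − a the rest, and s the proportion of episodes that are serious. Then:
- 90-day incidence = 1 − exp(−a)
- tabulated = 1 − exp(−(a + s·b))
- 1-year incidence = 1 − exp(−(a + b)) = 30%

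Constant rate: a = 0.3567 × 90/365 = 0.0879, b = 0.2687. Early-weighted: 70% of the hazard by Day 90, a = 0.2497, b = 0.1070.

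| Timing | 90-day | Tabulated, s = 0.1 | s = 0.3 | s = 0.5 | 1-year |
|---|---|---|---|---|---|
| Constant rate | 8.4% | 10.8% | 15.5% | 19.9% | 30% |
| 70% by Day 90 | 22.1% | 22.9% | 24.6% | 26.2% | 30% |

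For example, constant rate with s = 0.3: 1 − exp(−(0.0879 + 0.3 × 0.2687)) = 1 − exp(−0.1686) = 15.5%.

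**4. Severe AEs and SAEs at subject level (assumed rates).** Per subject: 4 non-serious AEs to Day 90 and 2 later; 0.8 SAEs to Day 90 and 0.6 later; 60% of SAEs and 10% of non-serious AEs graded severe; Poisson counts.

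- Expected severe events: 90-day 0.6 × 0.8 + 0.1 × 4 = 0.88; as planned 0.6 × 1.4 + 0.1 × 4 = 1.24; full year 0.6 × 1.4 + 0.1 × 6 = 1.44.
- Subjects with a severe AE, 1 − exp(−mean): 58.5%, 71.1%, 76.3%.
- Subjects with an SAE: 1 − exp(−0.8) = 55.1% at 90 days, and 1 − exp(−1.4) = 75.3% both as planned and for the full year.

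The SAE summaries (i.e and v) therefore equal the 1-year value, while the severe-AE figure falls between the two references.

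**The case against.** The split is deliberate, disclosed and consistent across Protocol 6.13.2, 6.13.7 and 9.9.1 and SAP 7.2. Both groups follow it, and no hypothesis is tested. The listings carry onset day and SAE status, so a reader could rebuild a 90-day subset. All of this stands, and it limits the point to what the tabulated rates mean. It does not supply the missing window in the tables.

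Four stronger readings are tempting, and the documents do not support them.

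- **That the tables overstate severity.** Against full 1-year reporting the rule can only leave events out, so the percentage of subjects with a severe AE is equal or too low. It is too high only if read as a 90-day figure.
- **That they overstate seriousness.** The percentage of subjects with an SAE has a defined 1-year window and is unaffected. The serious share of all episodes is raised (25.9% as planned, against 16.7% at 90 days and 18.9% for the full year, under the rates in step 4), but the SAP plans no such output.
- **That Protocol 6.13.3 conflicts with the 90-day rule.** It says "All AEs are collected from the time of transplanted lung reperfusion through subject participation duration (1 year post-operative"), but this concerns collection at the site, and the section points to 6.13.7 for reporting.
- **That the secondary objective promises all non-serious events to 1 year.** The item refers to the whole of participation, but it sits under a stem about short-term safety and is limited to what is reported through AEs. The scope is loose and worth stating, but it is not a clear breach.

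A further fair objection is that simply cutting every all-AE table at Day 90 would remove late SAEs from all relationship, severity and withdrawal summaries, since table v is by SOC and PT only. That stands, and the fix allows for it.

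**Conclusion.** The point holds for summaries i.a to i.d, ii, iii, iv and vi. Followed as written, they give percentages that belong to no single period: at or above the 90-day incidence and at or below the 1-year incidence for having the event at all. That ordering follows from the reporting rule alone.

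The size of the gap rests on assumed rates. For an event with 30% 1-year incidence it runs from under 1 percentage point above the 90-day figure (early-weighted, 10% serious: 22.9% against 22.1%) to about 11.5 points (constant rate, 50% serious: 19.9% against 8.4%). The corresponding shortfalls against 1 year are about 7 and 10 points.

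A reader might infer that the AE results are unusable as safety evidence, or that they favour one group. Neither follows: i.e and v are sound 1-year summaries, and both groups are treated alike. The consequence is that the all-AE rates cannot be taken at face value as a 90-day or 1-year safety profile, or carried into a later study as Control parameters, until the window is fixed. It should be corrected because the correction is cheap.

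**What to change.** Change SAP 7.2.5 only:

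1. Present the all-AE summaries (i.a to i.d, ii, iii, iv) for events with onset Day 0 to 90.
2. Present SAEs (i.e, v) for onset Day 0 to 90 and again for Day 0 to 1 year. Add 1-year SAE tables by relationship and by greatest severity, so that no late SAE drops out of those views.
3. Present withdrawals (vi) as all AEs with onset to Day 90 and SAEs with onset to 1 year.
4. State the onset window in each table title.
5. State in the SAP that the AE secondary endpoint is assessed as all AEs to 90 days and SAEs to 1 year.

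The reporting rule itself can stay. Protocol 9.1 allows changes to the statistical methods before database lock to be documented in the SAP without a protocol amendment, so neither the secondary objective nor 6.13.3 needs rewording. The cost is a date filter and a few extra SAE tables. Onset day is already in the planned listing, and no new data are needed.

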7.2.1 Intervention-emergent Adverse Events

Intervention-emergent AEs will be defined as those events, which are newly occurring or worsening from Baseline (Day 0). In all cases, only intervention-emergent AEs will be summarized.

7.2.2 Adverse Event Severity

The Investigator will use the following scale to grade the severity of any AEs:

- **Mild:** no intervention required; no impact on activities of daily living (ADL)
- **Moderate:** minimal, local, or non-invasive intervention indicated; moderate impact on ADL
- **Severe:** significant symptoms requiring invasive intervention; subject seeks medical attention, needs major assistance with ADL

7.2.3 Adverse Event Relationship to Study Intervention

The relationship of an AE to EVLP procedure and lung transplant will be assessed by the Investigator using the following guidelines:

- **Related:** The event is associated with the use of the investigational device or with procedures beyond a reasonable doubt.
- **Possibly Related:** The relationship with the use of the investigational device or procedure is weak but cannot be ruled out completely; alternative causes are also possible.
- **Unlikely:** The relationship with the use of the investigational device or procedures seems not relevant and/or the event can be reasonably explained by another cause, but additional information may be obtained.
- **Not related:** There is no temporal relationship between the investigational device or procedure and the event onset, an alternate etiology has been established.

7.2.4 Serious Adverse Events

A serious adverse event (SAE) is defined by federal regulation as any AE that results in any of the following outcomes: death, life-threatening AE, hospitalization or prolongation of existing hospitalization, a persistent or significant disability/incapacity, or a congenital anomaly/birth defect.

Important medical events that may not result in death, be life threatening, or require hospitalization may be considered an SAE when, based upon appropriate medical judgment, they may jeopardize the subject and may require medical or surgical intervention to prevent one of the outcomes listed

in this definition. Examples of such medical events include allergic bronchospasm requiring intensive treatment in an emergency room or at home, blood dyscrasias or convulsions that do not result in inpatient hospitalization, or the development of drug dependency or drug abuse.

7.2.5 Adverse Event Summaries

Adverse events and medical conditions will be coded using the Medical Dictionary for Regulatory Activities (MedDRA) coding dictionary. For intervention-emergent AEs, the following will be summarized and presented by Transplant Group for the FAS:

- i. An overall summary of Intervention-emergent AEs, which includes:
 - a. the number and percentage of subjects experiencing an intervention-emergent AE
 - b. the number and percentage of subjects experiencing an intervention-emergent AE by greatest severity
 - c. the number and percentage of subjects experiencing an intervention-emergent AE by strongest relationship to lung transplant
 - d. the number and percentage of subjects experiencing an intervention-emergent AE by strongest relationship to study intervention
 - e. the number and percentage of subjects experiencing an Intervention-emergent SAE
- ii. the number and percentage of subjects experiencing an intervention-emergent AE by SOC and PT
- iii. the number and percentage of subjects experiencing an intervention-emergent AE by SOC, PT, and strongest relationship to study intervention
- iv. the number and percentage of subjects experiencing an intervention-emergent AE by SOC, PT, and greatest severity
- v. the number and percentage of subjects experiencing an intervention-emergent SAE by SOC and PT
- vi. the number and percentage of subjects experiencing an intervention-emergent AE leading to study withdrawal by SOC and PT

In the overall summary of intervention-emergent AEs table (i), besides tabulating the number and percentage of subjects, the total number of Intervention-emergent AE episodes will also be provided. If a subject has repeated episodes of a particular Intervention-emergent AE, all episodes will be counted in the summary table.

In the remaining summary tables, the incidence of intervention-emergent AEs will be calculated by dividing the number of subjects who have experienced the event by the total number of subjects in the FAS. Thus, the incidence of intervention-emergent AEs is shown in terms of the total number of subjects and not in terms of the total number of episodes. If a subject has repeated episodes of a particular intervention-emergent AE, only the most severe episode, or the episode with the strongest causal relationship to study intervention, will be counted in the summary tables.

A subject with more than one type of intervention-emergent AE in a particular SOC will be counted only once in the total of subjects experiencing intervention-emergent AEs in that particular SOC. Since a subject could have more than one type of intervention-emergent AE within a particular

SOC, the sum of subjects experiencing different intervention-emergent AEs within the SOC could appear larger than the total number of subjects experiencing Intervention-emergent AEs in that SOC. Similarly, a subject who has experienced an intervention-emergent AE in more than one SOC will be counted only once in the total number of subjects experiencing AEs in all SOCs.

All occurrences of all intervention-emergent AEs will be listed for each subject, grouped by Transplant Group. The listing will contain the following information: transplant group, verbatim term, SOC, PT, severity, relationship to study intervention, date and day of onset, date and day of resolution, treatment given to treat the adverse event, the outcome, whether the event was an SAE, whether it led to withdrawal, and whether it is an intervention-emergent AE. Listings will be sorted by subject identification number, onset date, SOC, and PT. If the onset date is completely missing, then these events will be presented first. If the onset date is missing a month or a day, then these events will be presented before any complete dates.

